4.3. Tertiary endpoints

- Cell-mediated immunogenicity (CMI) of the study vaccine in subsets of subjects from ZOSTER-006 only.
 - CMI in terms of frequencies of antigen-specific CD4 T cells at Months 0, 3, 14, 26 and 38
 - Frequencies of CD4 T cells with antigen-specific Interferon gamma (IFN-γ) and/or Interleukin-2 (IL-2) and/or Tumour Necrosis Factor alpha (TNF-α) and/or CD40 Ligand (CD40L) secretion/expression to glycoprotein E (gE) and VZV as determined by intracellular cytokine staining in a subset of subjects at Months 0, 3, 14, 26 and 38.

5. STUDY POPULATION

5.1. Total Vaccinated cohort

The TVC will include all subjects in the TVC in ZOSTER-006 or ZOSTER-022 who were enrolled at centres participating in ZOSTER-064. All subjects in the TVC in ZOSTER-006 or ZOSTER-022 who were enrolled at centres not participating in ZOSTER-064 will be excluded from the TVC.

5.2. Total Vaccinated cohort - diary card subset

The TVC diary card subset for analysis of reactogenicity will include all subjects in the TVC who were also included in the diary card subset in either the ZOSTER-006 or ZOSTER-022 studies.

5.3. Modified Total Vaccinated cohort

The mTVC will include all subjects in the mTVC in ZOSTER-006 or ZOSTER-022 who were enrolled at centres participating in ZOSTER-064.

5.4. According-To-Protocol cohort for analysis of immunogenicity

The ATP cohort for analysis of immunogenicity will consist of all subjects in the ATP cohort for analysis of immunogenicity in ZOSTER-006 or ZOSTER-022 who were enrolled at centres participating in ZOSTER-064.

For the immunogenicity tables where different timepoints are presented, the concept of "Adapted ATP cohort for immunogenicity" will be used to denote that for each timepoint, the corresponding ATP cohort for immunogenicity will be used.

More specifically,

- The analyses at the timepoints Month 0 and Month 3 will be based on the ATP cohort for immunogenicity Month 3;
- The analysis at the timepoint Month 14 will be based on the ATP cohort for immunogenicity Month 14;
- The analysis at the timepoint Month 26 will be based on the ATP cohort for immunogenicity Month 26;
- The analysis at the timepoint Month 38 will be based on the ATP cohort for immunogenicity Month 38;

For the analysis of humoral immunogenicity, ATP cohort is further defined as ATP cohort for immunogenicity – Humoral.

Similarly, for the analysis of cell mediated immunogenicity, ATP cohort is further defined as ATP cohort for immunogenicity – CMI.

6. STATISTICAL METHODS

6.1. Analysis of demographics

Centres that participated in ZOSTER-064 along with their corresponding centre numbers in ZOSTER-006 or ZOSTER-022 will be presented. The distribution of subjects across the study centres will be tabulated by vaccination group and country.

Demographic characteristics (age at first vaccination, gender, race, geographic ancestry and ethnicity) of each study cohort will be tabulated by vaccination group for each of the cohorts defined above. Demographic characteristics will also be tabulated by vaccination group and frailty status.

The mean age (including range and standard deviation) of subjects will be calculated overall, by vaccination group and by frailty status.

The distribution of subjects included in the study across sites will be tabulated overall and per vaccine group.

Frequency tables will be generated for categorical variables such as gender.

Mean, median and standard deviation will be provided for continuous data such as age.

No inferential analyses of demographic data or baseline characteristics are planned.

6.2. Primary Objective

6.2.1. Analysis of Frailty Status

The primary analysis will be based on the TVC.

The number of subjects in each frailty category will be presented by age group, gender and country.

Demographic characteristics will be presented by frailty status.

Details of the assignment of subjects to frailty categories are presented in section 7.1.

6.3. Secondary Objectives

6.3.1. SF-36 and EQ-5D

The quality of life questionnaires to be analysed in this study are the SF-36 and EQ-5D. The SF-36 health survey and the EQ-5D questionnaires were to be completed by all subjects at Months 0, 14, 26 and 38 in ZOSTER-006 and ZOSTER-022.

Basic summary statistics (N, Mean, Standard Deviation) of each of the 8 components of the SF-36 Questionnaire (Physical Functioning, Role Physical, Bodily Pain, General Health, Vitality, Social Functioning, Role Emotional and Mental Health) and the EQ-5D Utility and visual analogue scale (VAS) scores will be presented at each scheduled timepoint by country and age group.

In addition, a more detailed statistical analysis, including the median, quartiles and minimum and maximum values, of the 10 components will be presented by timepoint, age-category and gender and will be presented in a separate annex.

The EQ-5D utility will be based on country specific Time Trade-off (TTO) values for the analysis by country. The UK TTO will be used for countries for which there is no specific TTO.

Presenting the data by country will allow for comparison with normative values for those questionnaires in the general population of the countries participating in the study

This analysis will be based on the TVC.

6.3.1.1. Analysis of Completion of SF-36 and EQ-5D

Compliance with completion of both SF-36 and EQ-5D questionnaires will be summarised by country at each time point (Months 0, 14, 26 and 38) and overall. This compliance will be presented for the TVC and will include in the calculation both newly encoded and previously encoded questionnaires.

% Completion will be defined for each time point as follows:

% Completion = $100 \times N1 / N2$

Where:

N1 = number of subjects with a completed SF-36/EQ-5D questionnaire.

N2 = number of subjects for whom a questionnaire was expected.

6.3.2. Vaccine efficacy by frailty status

The vaccine efficacy (VE) of the combined ZOSTER-006 and ZOSTER-022 studies will be based on the mTVC and will be classified by frailty status.

The VE will be estimated separately for each frailty category.

Further details of the model used to calculate the VE is contained in the statistical analysis plans (SAPs) for the ZOSTER-006 and ZOSTER-022 studies.

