1. INTRODUCTION

1.1. Background

Varicella-Zoster Virus (VZV) causes two distinct diseases. Varicella (chickenpox) shortly occurs after primary VZV infection and is characterised by systemic illness and a widely disseminated rash. Herpes Zoster (HZ, shingles) occurs when VZV reactivates from latency and typically manifests as a localised, dermatomal rash. The typical HZ rash usually lasts 2 to 4 weeks and is usually accompanied by pain; that is often described as burning, shooting, or stabbing, and pruritus, which can also be severe, may be as common as pain. In some patients, even touching the affected area lightly may cause severe pain, a phenomenon known as allodynia. The most common complication of HZ is postherpetic neuralgia (PHN), defined as pain that persists after the resolution of the HZ rash. Patients affected by PHN typically report constant burning, throbbing, intermittent sharp or electric shock-like pain, or allodynia. PHN tends to improve over a period of months and about 70-80% of cases resolve within 1 year. However, in some persons PHN persists for many years [Dworkin, 2007].

Inclusion of subjects in clinical trials may be biased for various reasons, e.g. inclusion/exclusion criteria, selection of patients by investigators, self-selection of patients. As such, the aim of this study is to explore if the subjects in the ZOSTER-006 and ZOSTER-022 studies were representative of an older adult population. This will be done by exploring the baseline frailty status and quality of life scores of subjects within the studies.

Several studies have demonstrated that the incidence and severity of HZ increases with age [CDC, 2008]. It is also likely that the incidence and severity of HZ is higher in frail subjects. However, as with age vaccine efficacy may somewhat lower in frail subjects. This study will therefore allow a synthesis of the benefit of vaccination in frail subjects, i.e. in terms of increased incidence, vaccine efficacy, safety and immunogenicity.

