10.8. Interpretation of analyses

Comparative analyses will be descriptive with the aim to characterise the difference between groups in the endpoint related to the objective. These descriptive analyses should be interpreted with caution.

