3.2. Secondary objectives

- To present the distribution of *SF-36* and *EQ-5D* scores in subjects included in ZOSTER-006 and ZOSTER-022 at baseline by country to allow comparison with normative values for those questionnaires in the general population of the countries participating in the study.
- To assess vaccine efficacy (VE) against HZ by frailty status.
- To assess HZ burden of illness (BOI) by frailty status.
- To identify predictive factors for individuals developing HZ.
- To describe safety by frailty status.
- To assess humoral immunogenicity by frailty status.

Tertiary

• To describe CMI by frailty status of subjects enrolled in ZOSTER-006 only.

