6.3.3. HZ Burden of illness by frailty status

The pooled HZ burden of illness (BOI) scores from the ZOSTER-006 and ZOSTER-022 studies will be presented by frailty category.

The number of subjects with a confirmed HZ episode, the mean BOI scores and the total follow-up time will be presented by Frailty category and vaccination group. The burden of illness vaccine efficacy and 95% confidence intervals (CIs) will be presented by frailty category. This analysis will be carried out for subjects in the mTVC.

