7.6. Number of Decimals

The following decimal description from the decision rules will be used for the demography, QoL and safety/reactogenicity analysis.

Display Table	Parameters	Number of decimal
		digits
Demographic	Mean, median age	1
characteristics		
Demographic	SD (age)	2
characteristics		
QoL	SF-36 Components, including LL & UL of CI	2
	EQ-5D Utility Scores, including LL & UL of CI	3
	EQ-5D VAS Scores, including LL & UL of CI	1
Reactogenicity	Mean, Min, Q1, Median, Q3, Max for duration	1
All summaries	% of count, including LL & UL of CI	1
All summaries	% of difference, including LL & UL of CI	2
Efficacy	VE, including LL & UL of CI	2
	IR	2
	T, T/N	1
	p-value	4

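### VE and burden-of-illness VE are planned only within each frailty category, with no direct estimate and CI of how efficacy differs between categories

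*SAP*

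**What the plan says.** The secondary objective is "To assess vaccine efficacy (VE) against HZ by frailty status" (SAP 3.2). For VE against HZ, SAP 6.3.2 states "The VE will be estimated separately for each frailty category", on the mTVC. For the model it adds only: "Further details of the model used to calculate the VE is contained in the statistical analysis plans (SAPs) for the ZOSTER-006 and ZOSTER-022 studies". Those parent-trial SAPs are not part of the documents. For burden of illness, SAP 6.3.3 states "The burden of illness vaccine efficacy and 95% confidence intervals (CIs) will be presented by frailty category". The decimals table in SAP 7.6 has an efficacy row for "VE, including LL & UL of CI", so each category VE will carry limits.

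Protocol 10.7.6.2.1 and 10.7.6.2.2 say only that the two efficacies are summarised or analysed by frailty status. On the reason for looking, Protocol 1.1 says: "However, as with age vaccine efficacy may somewhat lower in frail subjects". On interpretation, Protocol 10.8 says: "Comparative analyses will be descriptive with the aim to characterise the difference between groups in the endpoint related to the objective", and asks for caution in reading the results. No section of either document specifies a vaccine-by-frailty term, a ratio of rate ratios, a trend across categories, or a difference in VE or BOI VE with a CI.

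**The concern.** Whether efficacy is lower in frail subjects is a question about a difference between categories. Three separate VEs with three intervals do not estimate that difference or its uncertainty. The reader is left to see whether the intervals overlap, and overlapping 95% CIs are compatible with a clear difference. The frail category is small: SAP 6.3.6.2 expects about 5% of subjects to be frail. Its interval will be wide and will easily overlap the non-frail one. The risk is that an uninformative overlap is taken as maintained efficacy, without a statement of how large a loss relative to non-frail subjects the data still allow.

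**Working it through.** **The plan's own figure.** The documents give no power, event count or precision for VE by frailty. The only sample-size arithmetic is in Protocol 10.4: 30,000 enrolled - 1,000 suspected cases = 29,000 to be encoded. It reproduces, but has no bearing on this point.

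**Inputs from the documents**
- 29,305 subjects: pooled TVC of the two parent trials, from section 5.1 of the November 2018 SAP text. It is an upper bound for the mTVC at participating centres.
- 10 cases per 1000 person-years: Protocol 1.1.1, for people aged 60 and over. The same section gives about 5 for ages 50-59, so applying 10 to everyone is generous.
- About 5% frail: SAP 6.3.6.2, stated for the CMI subset.

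**Assumptions not in the documents**
- 1:1 allocation; about 35 months of follow-up (2.917 years).
- Frail share 5% or 10%; non-frail share 40% or 55%.
- Frail incidence 1.0 or 1.5 times the non-frail rate.
- The VE pairs shown below.

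**Formulas** (Poisson approximation on the log scale)
- Placebo cases in a category: P = 29,305 × share / 2 × 2.917 × rate. Vaccine cases: V = P × (1 - VE).
- SE of log(1-VE) = √(1/P + 1/V).
- Contrast: log[(1-VE frail)/(1-VE non-frail)], with SE = √(SE_f² + SE_n²).
- Power of the contrast: two-sided Wald test at 0.05.
- Probability that the two 95% CIs do not overlap: Φ{[|log ratio| - 1.96(SE_f + SE_n)] / SE}.

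**One case in full** (5% frail, 40% non-frail, equal incidence, VE 70% frail and 90% non-frail)
- Frail: P = 29,305 × 0.05 / 2 × 2.917 × 0.010 = 21.4; V = 6.4; SE_f = √(1/21.4 + 1/6.4) = 0.450. CI for VE: 27% to 88%.
- Non-frail: P = 170.9; V = 17.1; SE_n = √(1/170.9 + 1/17.1) = 0.254. CI for VE: 84% to 94%.
- The two CIs overlap.
- Ratio of (1-VE) = 0.30/0.10 = 3.00; SE = √(0.450² + 0.254²) = 0.517; CI = 3.00 times/divided by 2.75, or 1.09 to 8.26. The contrast excludes equality.
- Power: Φ(1.099/0.517 - 1.96) = 57%. Non-overlap: Φ{[1.099 - 1.96 × 0.704]/0.517} = 29%.

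**Range over the eight combinations of shares and incidence**

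| VE non-frail vs frail | Direct contrast | Non-overlapping CIs |
|---|---|---|
| 90% vs 80% | 22-46% | 8-19% |
| 90% vs 70% | 57-90% | 29-69% |
| 70% vs 50% | 24-52% | 9-24% |

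If VE is 90% in both categories, the CI of the ratio is the estimate times/divided by 2.5 to 4.4.

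**Sparse cases.** At 5% frail, equal incidence and VE 90%, the expected number of frail vaccine cases is 21.4 × 0.10 = 2.1, so the chance of none is exp(-2.14), about 12%. A Wald contrast then cannot be computed.

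**The case against.** The plan is declared exploratory (Protocol 10.7) and descriptive (Protocol 10.8), the objective is to assess VE by frailty status, and no objective tests heterogeneity. The lower limit of the frail VE already gives the lowest absolute efficacy in frail subjects compatible with the data, and Protocol 1.1 asks for a synthesis of benefit in that group. All of this stands. It does not remove the gap, because a ratio with a CI is itself descriptive and is the quantity that Protocol 10.8 asks for when groups are compared. The SAP rules out inferential analysis for demographic, humoral and CMI data, but not for VE.

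A reader might infer that the study cannot show lower efficacy in frail subjects. The documents do not support that. The categories contain different subjects and VE is reported with limits, so the ratio can be approximated from the published intervals, and a large difference could be visible. The approximation fails if a category has no vaccine cases.

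A reader might also infer that age is ignored in the VE analysis. That cannot be judged: the VE model is in parent-trial SAPs that are not supplied. A frailty contrast in those SAPs cannot be strictly excluded either, but they are cited here only for how VE is calculated. Nor do the documents rank VE by frailty above the other secondary objectives.

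Finally, the contrast will be weak for a modest loss, and the protocol speaks only of somewhat lower efficacy. That is true, and it is a reason to print the interval.

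**Conclusion.** The point holds as a gap in estimation. Both efficacy analyses stop at category-specific results, so the protocol's question about lower efficacy in frail subjects is left to informal comparison of separate CIs. In every scenario examined that comparison was clearly less sensitive than a direct contrast: 29-69% against 57-90% for VE 90% versus 70%. The contrast would not settle a modest difference (22-46% for 90% versus 80%). The ordering of the two approaches is firm; the percentages rest on the listed assumptions and a large-sample approximation that is rough with so few frail vaccine cases. No figure was derived for BOI VE, since its method is in documents not supplied; there the conclusion rests on the text alone. This is a worthwhile, cheap addition to an exploratory analysis and does not invalidate the category results.

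**What to change.** In SAP 6.3.2, keep the category VEs and add, labelled descriptive:
- the ratio of (1-VE) for pre-frail and for frail versus non-frail, with 95% CIs, from one pooled mTVC model with a vaccine-by-frailty-category term and the same stratification as the parent-trial VE model, which should be stated here;
- an exact or penalised (Firth-type) method for that ratio, because frail vaccine cases may be few or zero;
- a supportive model with a vaccine-by-continuous-frailty-index term, using the index already derived in SAP 7.3.

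In SAP 6.3.3, add the difference in BOI VE between categories with a CI, for example by bootstrap.

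State that the frail contrast is expected to be imprecise (a CI of roughly times/divided by 2.5 to 4.4 if VE is 90% in both categories, under the assumptions above) and that similar point estimates do not show maintained efficacy.

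The cost is a short SAP edit, two further models and a bootstrap on existing data. The downside is a wide interval in the report, which the added statement explains.

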6.3.3. HZ Burden of illness by frailty status

The pooled HZ burden of illness (BOI) scores from the ZOSTER-006 and ZOSTER-022 studies will be presented by frailty category.

The number of subjects with a confirmed HZ episode, the mean BOI scores and the total follow-up time will be presented by Frailty category and vaccination group. The burden of illness vaccine efficacy and 95% confidence intervals (CIs) will be presented by frailty category. This analysis will be carried out for subjects in the mTVC.

6.3.4. Predictive factors for subjects developing HZ

A Cox regression model allowing for time-dependent covariates will be fitted to identify which factors are predictive of developing HZ. The model will include time to HZ as the outcome variable, the demographic variables age and gender and the time dependent *SF*-36 variables and *EQ-5D* variables as potential predictors. This analysis will be performed for subjects in the Placebo group in the TVC.

Subjects who did not develop HZ will be censored at the time of their last study visit. The regression model will be used for both minimally adjusted analyses and multivariate analyses. All factors will initially be examined in an age- and gender-adjusted model with further adjustment for the original study (ZOSTER-006 or ZOSTER-022). Factors will be included in the multivariate model if they are associated (P < 0.05 using a two-sided Wald test) with HZ in the minimally adjusted model. The multivariate model will also include age, gender and original study. A step-down (backward) variable selection procedure will be used to fit the final multivariate model. This model will be fitted using the PHREG procedure of the SAS/STAT package.

The parameter estimates and standard error of each SF-36 and EQ-5D parameter from the minimally adjusted model will be presented. The final multivariate model will also be presented.

The analysis will be performed with the event defined as a HZ confirmed case. Three separate analyses will be performed examining the impact of excluding suspected but not confirmed cases.

The first analysis will exclude subjects who had a suspected case that was later proven not to be a HZ episode.

204878 (ZOSTER-064) Statistical Analysis Plan Amendment 1

The second analysis will include all subjects. Those subjects who had a suspected case that was later proven not to be a HZ episode will be censored at their latest available assessment and will be considered not to have had the event.

The third analysis will also include all subjects. The definition of event will be changed to having a suspected case of HZ.

The distribution of confirmed cases of HZ amongst suspected cases will be presented by age group for subjects in the placebo group in the TVC.

Details of the process behind the inclusion of time dependent covariates are included in section 7.4

